12.3 Handling of missing data

For primary analysis, data will be presented using all observed data at the given time point of analysis.

No multiple imputation or Mixed Models for Repeated Measures (MMRMS) will be considered since the influence of up-titrators in each group population violates the MAR assumption.

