- Group 2: secukinumab 150 mg (1mL) once every four weeks till (and including) Week 256. After approval and implementation of Amendment 1, patients may be escalated to 300 mg as judged appropriate by the investigator.

Study treatment dose adjustments are not permitted until Week 156.

Starting from Week 156 (i.e. during the open label study period), after approval and implementation of Amendment 1, the secukinumab dose should be escalated from 75 mg to 150 mg for patients whose signs and symptoms are not fully controlled with the current dose of 75 mg, and may improve with higher dose as judged by the investigator.

Further, the dose should also be escalated to 300 mg for patients currently on 75 mg or 150 mg, and whose signs and symptoms are not fully controlled and may improve further with an increase in dose as judged by the investigator.

Dose escalation from secukinumab 75 mg to 300 mg can be done either in one step or in two steps (first 150 mg, then 300 mg based on investigator's judgement).

For patients escalated to 150 mg or 300 mg, no dose reduction can be performed at a later stage.

Subjects will continue to be on background methotrexate (MTX) (if they were already taking MTX at the start of core study CAIN457F2306) throughout the study. The dose of MTX may be adjusted as deemed appropriate by the investigator.

In addition subjects will be allowed to start or adjust the dose of corticosteroids and non-steroidal anti-inflammatory drugs (NSAIDs) as deemed appropriate by the investigator.

[figure not shown]
Before enrolment in this extension study, all subjects electing to continue will sign an Informed Consent form. After approval and implementation of Amendment 1, all subjects electing to continue will sign a new version of the Informed Consent form. Detailed instructions for self-administration of the s.c injection using the PFS formulation will be provided to each subject. Each injection will be administered into an appropriate injection site of the body. For the first 6 months of the extension study (up to Week 128), all injections will be performed at site. Starting from Week 132 subjects will have the choice of self-administration at home or continuing with administration at site, based on personal preference and the investigator's clinical judgment. Site staff or caregiver (once trained) will administer the injection to subjects who are not able or feel insecure to self-administer the PFS injection.

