On-site visits to assess safety and efficacy will be scheduled at 4-16 week intervals during the study. Assessments for safety, efficacy, PK [REDACTED] will be performed according to the assessment schedule.

Efficacy assessments will be performed at regular intervals in this study, and after careful evaluation of disease status/activity, investigators should discontinue subjects who are deemed not to be benefiting from the study treatment, based on lack of improvement or worsening of their symptoms. Moreover, subjects are free to discontinue participation in the study at any time for lack of efficacy or for any other reason.

[REDACTED]

Figure 3-1 Extension Study (CAIN457F2306E1) design

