5.5.9 Discontinuation of study treatment and premature subject withdrawal

Study treatment must be discontinued if the investigator determines that its continuation would result in a significant safety risk for a subject. The following circumstances require study treatment discontinuation:

- Withdrawal of informed consent
- Emergence of the following adverse events:
 - Any severe or serious adverse event that is not compatible with administration of study medication, including adverse events that require treatment with an unacceptable co-medication
 - Onset of lymphoproliferative disease or any malignancy except for treated basal cell carcinoma, treated actinic keratoses, treated in situ carcinoma of the cervix or non-invasive malignant colon polyps which are being or have been removed
 - Life-threatening infection
- Any laboratory abnormalities that in the judgment of the investigator are clinically significant and are deemed to place the subject at a safety risk for continuation in the study (A general guidance on clinically notable laboratory values is provided in [Appendix 1](#)).
- Pregnancy
- Use of any biologic immunomodulating agent except secukinumab

- Any protocol deviation that results in a significant risk to the subject's safety

In addition to the requirements mentioned above for study treatment discontinuation, the investigator should discontinue study treatment for a given subject if there is a lack of improvement or worsening of their symptoms, or if, on balance, he/she believes that continuation would be detrimental to the subject's well-being.

For subjects who discontinue study treatment a Dosage Administration Record eCRF should be completed, giving the date and primary reason for stopping study treatment.

The investigator must also interact with the IRT to register the subject's discontinuation from study treatment.

Subjects may voluntarily withdraw from the study for any reason at any time. They may be considered withdrawn if they state an intention to withdraw, fail to return for visits, or become lost to follow-up for any other reason.

If premature withdrawal occurs for any reason, the investigator must make every effort to determine the primary reason for a subject's premature withdrawal from the study and record this information on the appropriate Study Phase Disposition CRF.

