9.4.3 Handling of missing values/censoring/discontinuations

Efficacy data will be presented using all available data at the given time point of analysis.

Additionally, under the assumption of missing at random, multiple imputation by treatment may be performed for all baseline and post-baseline efficacy variables of interest during the trial.

Continuous variables will be analyzed using a mixed-effects model repeated measures (MMRM) which is valid under the missing at random (MAR) assumption. For analyses of these parameters, if all extension post-baseline values are missing then these missing values will not be imputed and this subject will be removed from the analysis of the corresponding variable, i.e. it might be that the number of subjects providing data to an analysis is smaller than the number of subjects in the FAS.

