9.4.4 Supportive analyses

Sensitivity analyses may be performed to assess the robustness of missing data handling. This may include multiple imputation for ACR20/50.

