NSAID	Non-Steroidal Anti-Inflammatory Drug
NovDTD	Novartis Drug/Therapy Dictionary
████	████████████████████
PDS	Programming and Dataset Specifications
PFS	Pre-filled Syringe
PK	Pharmacokinetic
PoC	Proof of Concept
PRO	Patient Reported Outcome
PsA	Psoriatic Arthritis
QoL	Quality of Life
RA	Rheumatoid Arthritis
RBC	Red blood cells
RDC	Remote Data Capture
RF	Rheumatoid Factor
SAE	serious adverse event
s.c.	Subcutaneous
████	██
SJC	Swollen joint count
SpA	Spondyloarthritis
SUSAR	Suspected Unexpected Serious Adverse Reaction
TJC	Tender joint count
TNF	Tumor Necrosis Factor
TNF α -IR	TNF α Inhibitor Incomplete/Inadequate Responders
ULN	Upper Limit of Normal
UPT	Urine Pregnancy Test
VAS	Visual Analog Scale

WBC White blood cells

1 Introduction

Data will be analyzed by Novartis according to the data analysis section 9 of the study protocol. That statistical methodology is described below and any deviations from the protocol are documented. Additional detailed information regarding the analysis methodology is contained in the Appendix section.

2 Changes to statistical methods planned in the protocol

No multiple imputation techniques and no MMRM estimation will be performed due to the presence of up-titrators.

[figure not shown]
3 Study objectives

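### The SAP rules out the optional missing-data check on ACR20/50/70 and names no substitute, so observed-case rates at Weeks 208 and 260 may overstate response in the extension FAS

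*SAP*

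**What the plan says.** **Protocol.** Section 9.4.3 presents efficacy on all available data. It then adds, under missing at random (MAR), that "multiple imputation by treatment may be performed for all baseline and post-baseline efficacy variables of interest during the trial". It plans a mixed model for repeated measures (MMRM) for continuous variables. Section 9.4.4 adds: "Sensitivity analyses may be performed to assess the robustness of missing data handling", and gives multiple imputation (MI) for ACR20/50 as an example.

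**SAP.** Section 2 declares the change: "No multiple imputation techniques and no MMRM estimation will be performed due to the presence of up-titrators". Section 12.3 keeps the observed-case rule, "For primary analysis, data will be presented using all observed data at the given time point of analysis", and gives the reason for dropping MI and MMRM: "since the influence of up-titrators in each group population violates the MAR assumption". No other method follows. Section 12.4 repeats that efficacy on the FAS rests on observed data.

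**Who leaves, and what is collected.** Protocol 3.1 says that "investigators should discontinue subjects who are deemed not to be benefiting from the study treatment". Section 5.5.9 says that "the investigator should discontinue study treatment for a given subject if there is a lack of improvement or worsening of their symptoms". Leavers have an end-of-treatment (EoT) visit four weeks after the last dose, with the assessments of the final visit of their current period (5.5.9, 5.5.11 and 6). A follow-up visit comes 12 weeks after the last dose. In Table 6-3 the Week 268 column has no joint counts, VAS scores or HAQ-DI, so ACR cannot be derived there. After Week 104 the SAP uses the recorded nominal visit (Section 7).

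**The concern.** The primary objective is long-term ACR response up to Week 260. No hypothesis is tested, so the by-visit rates and their intervals are the result. A subject who stops for lack of benefit stays in the extension FAS but contributes no ACR after the EoT visit. If such subjects respond less often than those who remain, the observed rate can look maintained because its denominator shrinks.

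The SAP's reason does not cover this. Escalation may be a reason not to model by assigned dose, but it does not make values missing. It also cannot affect the visits before Week 156: "Study treatment dose adjustments are not permitted until Week 156". If MAR is doubted, the observed proportion is not a safer estimate for the FAS. It needs missingness unrelated to response, which is a stronger assumption than MAR.

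**Working it through.** **The plan's own figures.** The documents give no dropout assumption for the extension and no figure for missing ACR. The only sample-size statement, 460 to 520 eligible subjects, reproduces with the 400 secukinumab and 200 placebo subjects that its counts imply: 0.8 × 400 + 0.7 × 200 = 460 and 0.9 × 400 + 0.8 × 200 = 520. It is not in dispute.

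**Who is missing at which visit.** Under the nominal-visit rule, Period 3 leavers who attend EoT count at Week 156, Period 4 leavers at Week 208 and Period 5 leavers at Week 260. So Week 208 lacks mainly Period 3 leavers, and Week 260 lacks mainly Period 3 and 4 leavers. For Period 5, Sections 5.5.11 and 6 name Week 260. The Table 6-3 heading instead places discontinuation over Week 268, and its footnote prints Week 1260. SAP 17.1 also has an example that re-aligns a Week 112 visit. I take the nominal-visit rule, which both SAP 7 and 17.1 state, as governing.

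**Inputs.** p = 46.4% (150 mg) or 35.5% (75 mg), the Week 104 ACR50 rates in the Amendment 1 rationale, used as illustrative completer rates. D = total extension dropout, assumed 10, 20 or 30% and spread evenly over three periods. f = leavers' response rate as a fraction of p. Period 5 leavers (D/3) are counted at Week 260.

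**Formulas for Week 260.**
- Observed rate = [(1 − D)p + (D/3)fp] / (1 − 2D/3)
- FAS rate = (1 − D)p + Dfp
- Overstatement = observed rate − FAS rate

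Example with p = 0.464, D = 0.20, f = 0: observed 0.3712 / 0.8667 = 42.8%, FAS 37.1%, overstatement 5.7 points.

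| Completer rate | Leavers' response | D = 10% | D = 20% | D = 30% |
|---|---|---|---|---|
| 46.4% | none | 3.0 | 5.7 | 8.1 |
| 46.4% | half of p | 1.5 | 2.9 | 4.1 |
| 46.4% | same as p | 0 | 0 | 0 |
| 35.5% | none | 2.3 | 4.4 | 6.2 |
| 35.5% | half of p | 1.1 | 2.2 | 3.1 |

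**Week 208.** Only Period 3 leavers are missing. If p applies to those still on treatment and f = 0, the overstatement is (1 − 2D/3)p × (D/3) / (1 − D/3). At D = 20% and p = 0.464 this is 0.8667 × 0.464 × 0.0667 / 0.9333 = 2.9 points.

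**Documented attrition.** Amendment 1 reports 460 enrolled and 432 still on treatment in September 2015: 28/460 = 6.1%. If all 28 lacked ACR at a visit and none responded, with 46.4% as the observed rate, the overstatement is 0.464 × 0.0609 = 2.8 points. For 35.5% it is 2.2. This bounds the effect of those 28 subjects only; it is not the share missing at Week 260.

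**Scale.** The SAP's continuity-corrected score interval at 46.4% with an assumed 230 observed subjects is 39.9 to 53.1%, a half-width of 6.6 points.

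**The case against.** The strongest reply is that the SAP removed nothing to which the protocol had committed for ACR. Observed-case was the protocol's rule, MI was optional, and the change is declared openly. That stands. A reader might infer that a planned primary analysis was dropped, or that losing MMRM weakens the ACR analysis. The documents support neither: MMRM was planned, but for continuous variables only. What is lost is the only kind of ACR missing-data check that the protocol names.

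Second, the direction is not established. After Amendment 1, subjects who are not fully controlled can be escalated and so stay under observation, and some subjects leave for reasons unrelated to response. This also stands, and it limits the claim to a plausible direction.

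Third, some missingness is already handled. ESR replaces missing CRP, partial joint counts are scaled up, and ACRn tolerates two missing components. These rules help at attended visits but not at visits after exit.

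Fourth, harm is limited. The study is descriptive, and its subjects were already selected for benefit. Responder counts, individual listings and disposition with reasons are planned, so responders/N could be rebuilt by hand. That lowers the severity, but no planned table shows how far the rates depend on missing subjects.

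Finally, SAP 12.2 is absent from the available text and 12.4 is partly redacted, so the finding covers the readable SAP. Section 12.3 itself reads as complete.

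**Conclusion.** The point holds in a limited form. The readable SAP has no missing-data sensitivity analysis for the primary ACR20/50/70 rates. Exit is tied to lack of benefit, and ACR ends with one EoT visit. Rates at Weeks 208 and 260 may therefore overstate response in the extension FAS.

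The size cannot be derived from the documents. With a 46.4% completer rate, even dropout and Period 5 EoT data counted at Week 260, the overstatement is at most about 3.0, 5.7 and 8.1 points at 10, 20 and 30% dropout. It is about half that if leavers respond at half the completer rate, and zero if they respond alike. The only documented attrition corresponds to at most 2.8 points.

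A reader might simply multiply the observed rate by total dropout and report 0.464 × 0.20 = 9.3 or 0.464 × 0.30 = 13.9 points at Week 260. That treats every leaver as missing there, whereas Sections 5.5.11 and 6, with the nominal-visit rule, largely place Period 5 EoT data at Week 260. Nor do the documents show that the rates are in fact inflated. This is worth fixing because it affects how the primary result is read; error rates and power are not involved.

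**What to change.** Keep observed-case as the main display. Add one supplementary by-visit table of ACR20/50/70 for the extension visits at which ACR is assessed:

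- Use the fixed extension-FAS N in the two combined assigned-dose columns of SAP 5.1, and print n observed/N at each visit.
- Apply the existing ESR-substitution, joint-scaling and ACRn rules first.
- Use observed data at the nominal visit, including EoT data recorded there and data after escalation.
- Count every subject with no evaluable response as a non-responder.
- Label the table a conservative bound by assigned dose, regardless of escalation.

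The same table for the HAQ-DI and DAS28 responder endpoints is optional. Limit the MAR sentence in SAP 12.3 to explaining why MI and MMRM are not used. Reconcile the Table 6-3 heading and the Week 1260 footnote with protocol Section 6, and state in the SAP which analysis visit takes early Period 5 EoT data.

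The cost is some wording and one set of tables from existing data, with no modelling and no MAR assumption. The downside is that the added rates look less favourable, partly because some subjects are missing for reasons unrelated to response.

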12.4 Analysis of Primary Variable(s)

The primary efficacy variable(s) is the clinical response to treatment according to ACR20, ACR50 and ACR 70 improvement in disease activity over time up to Week 260.

ACR response criteria denote the response (i.e., improvement) in signs & symptoms of the disease of a subject compared to baseline of the core study.

The analysis of the primary variables will be based on the FAS. Primarily, CRP will be used instead of ESR to calculate ACR response; ESR will only be used in the event CRP is missing.

Shift tables will be provided comparing the subject's ACR evaluation at the pre up-titration visit relative to the observed data of the following week intervals after up-titration: (12-32 weeks), (36-56 weeks) and (60-80 weeks). The ACR grouping presented in the table will be: $ACR < 20$, $20 \leq ACR < 50$, $50 \leq ACR < 70$, $ACR \geq 70$.

Graphical representation (line plots) of ACR20, ACR50 and ACR70 response over time and Sankey-style bar chart for the ACR response within the subjects that up-titrated from 150 mg to 300 mg (provided that up-titration has been occurred for more than 8 weeks) will be drawn from the observed data.

Additionally, observed data tables will summarize the ACR20, ACR50 and ACR70 response following up-titration when assessed. Results will be illustrated in line plots.

Also individual subject listings of the ACR components as well as for the ACR20/50/70 response will be given.

Statistical model, hypothesis, and method of analysis

No formal hypotheses are planned for this study. The proportion of subjects meeting the ACR criteria (ACR20, ACR50, and ACR70) will be descriptively summarized for each treatment by absolute and relative frequencies followed by 95% confidence intervals for the proportion of patients responding to treatment according to the ACR criteria from Week 1 onwards based on the pooled data from core and extension study. Results regarding ACR20/50/70, will be presented overall in the FAS population as well as in subgroups by TNF α status (naive or IR) and by concomitant use of MTX as appropriately.

Placebo group (core study) in efficacy analysis will not be considered.

All the above efficacy variables will be analyzed on the FAS (unless otherwise specified) for all applicable analysis visits based on the observed data.

For binary variables, the proportion of responders along with the 95% CI will be presented by treatment groups over analysis visits.

For continuous variables, the change from baseline (of core) when available, will be summarized.

[REDACTED]

Figures will be provided for the following parameters:

- [REDACTED]
- DAS28-CRP and SF-36 PCS change from baseline.
- HAQ-DI score (change from baseline) overall and following the up-titration
- HAQ-DI response overall and following the up-titration
- HAQ-DI response by TNF- α inhibitor status.
- Remission response and low disease activity response according to DAS28-CRP
- [REDACTED].
- [REDACTED]

Individual listings will be considered for all efficacy variables of the study.

Joint/bone structural damage at Week 156, 208

The changes in joint/bone structural damage (total sharp score, and its components, erosion score and joint spacing narrowing score) will be summarized by the same treatment groups as follows using evaluable data of each x-ray reading session:

- Baseline to:
 - Week 24
 - Week 52
 - Week 104
 - Week 156
 - Week 208
- Week 24 to:
 - Week 52
 - Week 104
 - Week 156

[figure not shown]
- Week 208
- Week 52 to:
 - Week 104
 - Week 156
 - Week 208
- Week 104 to:
 - Week 156
 - Week 208

[figure not shown]
[figure not shown]
The above analyses will be done on both FAS and X-ray completers where X-ray completers are those subjects that had X-ray measures at baseline, Week 16/24, Week 52, Week 104, Week 156 and Week 208. Subgroup analyses by TNF-alpha inhibitor status will be provided.

Analyses will be performed for each reading campaign, as appropriate depending on the available data.

For the purpose of the campaign 3 the readings of baseline, week 156 and week 208 will be used for the analysis. Any data on week 260 will be shown only in listings.

Individual listings will be provided for Joint structural damage components.

13 Pharmacokinetic evaluations (change / add PD, PK/PD, Biomarkers, as needed)

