5.5.12 Early study termination

The study can be terminated at any time for any reason by Novartis. Should this be necessary, the subject should be seen as soon as possible and treated as a prematurely withdrawn subject. The investigator may be informed of additional procedures to be followed in order to ensure that adequate consideration is given to the protection of the subject's interests. The investigator will be responsible for informing IRBs and/or ECs of the early termination of the trial.

6 Visit schedule and assessments

Table 6-1, Table 6-2 and Table 6-3 list all of the assessments and indicate with an "X" when the visits are performed.

Subjects should be seen for all visits on the designated day or as close to it as possible. Subjects should not receive study medication within less than 2 weeks after the previous administration.

During the treatment periods, subjects may be seen at an unscheduled visit, e.g. if they experience deterioration of their condition, or AEs that in the opinion of the investigator need intervention or repeated laboratory testing. During these unscheduled visits, study treatment will not be administered. Subjects who discontinue study treatment will continue to be followed for safety assessments. They are not considered withdrawn from the study.

Subjects who discontinue study treatment before completing the study, and those who prematurely withdraw from the study for any reason should be scheduled for a study visit 4 weeks after their last study treatment administration, at which time all the assessments listed for EoT for the given treatment period (Week 156 or 208 or 260) will be performed (see [Section 5.5.9](#)). Subjects will then return to the study site 12 weeks after the last study treatment administration for further assessments as indicated under the follow-up visits (F268).

If they refuse to return for these assessments or are unable to do so, every effort should be made to contact them or a knowledgeable informant by telephone or by sending appropriate correspondence (i.e. certified letter) immediately. At this contact, the safety (e.g., potential occurrence of AE or SAE) and the primary reason for a subject's premature withdrawal should be determined.

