Extension Full analysis set (extension FAS): The extension FAS will be comprised of all subjects enrolled in the extension study and have at least one post baseline assessment of efficacy during the extension period. Subjects will be analyzed according to the treatment assigned to.

(In this document extension FAS is referred as to FAS).

Of note, FAS will comprise only the subjects from extension whereas safety set will include from core or extension, safety set will be larger than FAS.

Up-titration Subset: The up-titration subset will be comprised of subjects from the extension FAS set who received at least one dose of the up-titration dose.

Psoriasis subset: The psoriasis subset will include all FAS subject who have $\geq 3\%$ of the body surface area (BSA) affected by psoriatic skin involvement at baseline.

Nail subset: The nail subset will include all FAS subject who have psoriasis currently in nails at baseline.

Safety set: The safety set includes all subjects who took at least one dose of study treatment during the treatment period in core or extension study. Subjects will be evaluated according to treatment received.

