No visit windows were used in case of up-titrations. The before up-titration measurement is considered as the last visit measurement, performed on or before the date that patient took the up-titration dose. The up-titration data analysis will be based on week intervals; it is accounting for the time period between the actual date of exposure to the up-titrated dose and the last visit date of the subject:

- 4 – 8 weeks after up-titration
- 12 – 32 weeks after up-titration
- 36 – 56 weeks after up-titration
- 60 – 80 weeks after up-titration
- 84 – 104 weeks after up-titration

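### Two ACR displays after dose escalation, the 150-to-300 mg Sankey chart and the shift tables, leave out subjects who stop after one or two escalated doses

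*SAP*

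**What the plan says.** SAP section 5 defines the Up-titration Subset as extension FAS subjects "who received at least one dose of the up-titration dose". One escalated dose is enough to belong to it.

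SAP 12.4 then plans several ACR displays for escalators, and two of them are narrower than that subset:

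- The Sankey chart is a "Sankey-style bar chart for the ACR response within the subjects that up-titrated from 150 mg to 300 mg", with the restriction "provided that up-titration has been occurred for more than 8 weeks) will be drawn from the observed data".
- The shift tables compare the ACR category before escalation with the category in the "following week intervals after up-titration: (12-32 weeks), (36-56 weeks) and (60-80 weeks".

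SAP 17.1 lists five intervals for the up-titration analysis. The first is "4 – 8 weeks after up-titration" and the last runs from 84 to 104 weeks. The shift tables use neither of these two.

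On subjects who stop, Protocol section 6 says they "should be scheduled for a study visit 4 weeks after their last study treatment administration", with the full end-of-treatment assessments of the current period. Protocol 5.5.9 adds a follow-up visit 12 weeks after the last dose. It also says that "the investigator should discontinue study treatment for a given subject if there is a lack of improvement or worsening of their symptoms".

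**The concern.** Both displays select subjects by something that happens after escalation. The Sankey chart requires more than 8 weeks of up-titration, and the shift tables require an ACR value at 12 weeks or later. A reader will take them as a picture of what followed a dose increase, but they describe those who stayed long enough to be counted. Early stopping can be related to outcome, because poor response is one of the protocol's reasons for stopping.

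The omission does not come from missing data. An early stopper has an end-of-treatment ACR, and SAP 17.1 already defines an interval that would hold it. SAP 12.4 gives no reason for either cut-off. The study has no control group, and the SAP drops multiple imputation and MMRM, so no planned method would offset the selection within these displays.

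**Working it through.** **Inputs**

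- Four-weekly dosing up to Week 256 (Protocol 5.2).
- End-of-treatment visit 4 weeks after the last dose and follow-up visit 12 weeks after it (Protocol 5.5.9 and section 6).
- Routine site visits in the open-label period: Weeks 156, 168, 180, 192, 208, 220, 232, 244 and 260. Scheduled ACR visits: Weeks 156, 180, 208, 232 and 260 (Tables 6-1 to 6-3).
- Escalation may be decided at any on-site visit (Protocol 5.5.5).

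The plan states no figure to reproduce here.

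**Step 1. When an early stopper's ACR is measured.** After *k* escalated doses the last dose is 4(*k* − 1) weeks after the first, so the end-of-treatment visit falls at 4(*k* − 1) + 4 = 4*k* weeks:

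- *k* = 1: 4 weeks
- *k* = 2: 8 weeks
- *k* = 3: 12 weeks
- *k* = 4: 16 weeks

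The end-of-treatment assessments include joint counts, the VAS scales, HAQ-DI and hsCRP. Subjects with one or two escalated doses therefore have an ACR at 4 or 8 weeks, which is outside the shift-table intervals and not more than 8 weeks. From three doses on, the value falls in the 12-32 week interval.

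**Step 2. Whether the follow-up visit changes this.** It falls 4(*k* − 1) + 12 weeks after the first escalated dose: 12 weeks for *k* = 1 and 16 weeks for *k* = 2. Table 6-3 schedules no joint counts there, so it yields no ACR. If the 8-week rule means time from escalation to the last visit, an early stopper who attends follow-up could satisfy it. The shift tables would still omit that subject.

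**Step 3. When continuing subjects are first assessed.** Weeks from each routine site visit to the next scheduled ACR:

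| Escalated at | 156 | 168 | 180 | 192 | 208 | 220 | 232 | 244 |
|---|---|---|---|---|---|---|---|---|
| Weeks to next ACR | 24 | 12 | 28 | 16 | 24 | 12 | 28 | 16 |

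The minimum is 12. For subjects escalated at a routine visit, an ACR at 4-8 weeks thus comes essentially from an end-of-treatment visit. The exception is a subject dosed on site every 4 weeks who escalates at Week 172, 176, 200, 204, 224, 228, 252 or 256, which is 8 or 4 weeks before a scheduled ACR.

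**Step 4. How many are likely to be affected.** A subject escalated at Week 156 doses again at 160 and 164 and is next seen at 168. A stop at that visit follows three doses and gives an end-of-treatment ACR at 12 weeks. Routine site visits are 12 or 16 weeks apart, so the same holds for every routine escalation visit. Stopping after one or two doses needs an unscheduled contact, the subject's own withdrawal or extra on-site dosing.

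**Step 5. Illustrative size (assumed values only).** Let *d* be the share of escalators left out, *P* the true share improved among all escalators and *q* the share improved among those left out. The displayed share is (*P* − *dq*)/(1 − *d*). With *P* = 40% and *q* = 0:

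- *d* = 2%: 0.40/0.98 = 40.8%
- *d* = 5%: 0.40/0.95 = 42.1%
- *d* = 10%: 0.40/0.90 = 44.4%

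The other way round, if 40% of those kept and 20% of those left out improve, adding the latter back gives 39.6%, 39.0% and 38.0% at the same values of *d*. If *q* equals *P* there is no distortion, and if *q* exceeds *P* the display is too low.

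**The case against.** The case for leaving the text alone is substantial.

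- **The data are reported elsewhere.** SAP 12.4 also plans observed-data tables and line plots of ACR20/50/70 after up-titration with no minimum duration, plus individual listings. SAP 17.1 bases the up-titration analysis on intervals that start at 4-8 weeks. SAP 8.1 tabulates premature discontinuation with reasons, including for the up-titrated groups. The main analysis uses all observed FAS data. All of this stands.
- **The 8-week wording may not mean time on dose.** SAP 17.1 counts from the first escalated dose to the last visit, so some early stoppers could qualify for the chart. This stands as an ambiguity that the SAP should settle.
- **The 12-week start fits the visit schedule.** It equals the shortest routine gap to an ACR visit. The shift tables also omit the latest interval, so they do not cut only early data. This explains the choice, but still leaves early stoppers uncounted.
- **The 8-week rule may be about follow-up time.** Someone dosed on site who escalates at Week 252 or 256 has only 8 or 4 weeks before Week 260. This stands too: the rule does not remove early stoppers alone. A criterion based on escalation date would handle late escalation without removing them.

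A reader might infer that early failures vanish from the trial's results, or that the benefit of escalation is shown to be biased upward. The documents support neither. The first is contradicted by the other planned outputs. The second needs both an early-stopping rate and a lower response among those left out, and the documents give neither. Protocol 5.5.9 also lists reasons for stopping that need not reflect poor response, such as withdrawal of consent and pregnancy.

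**Conclusion.** The point holds for two descriptive displays only. On the plain reading, subjects who stop after one or two escalated doses are left out of the 150-to-300 mg Sankey chart and of the ACR shift tables, although their ACR is measured. If the 8-week rule means elapsed time, the Sankey part weakens but the shift-table part remains.

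The size cannot be computed, and the visit schedule suggests that few subjects are affected. The displayed response is too favourable only if those left out respond less often than those kept. That is plausible, since poor response is a reason to stop, but it is an assumption. With a true 40% and no improvement among those left out, the overstatement is 0.8 points at 2% early stopping, 2.1 at 5% and 4.4 at 10%. No hypothesis test or between-dose comparison depends on these displays. This is a minor, cheap improvement.

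**What to change.** In SAP 12.4:

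1. Replace the 8-week condition with all subjects in the Up-titration Subset for that dose step whose escalation date allowed the interval to be reached by Week 260. For the start of each interval this means escalation by Week 260 − 4 = 256, 260 − 12 = 248, 260 − 36 = 224 or 260 − 60 = 200.
2. In the Sankey chart and the shift tables, add a category for subjects who discontinued before the interval, with its count.
3. Add the 4-8 week interval of SAP 17.1 to the shift tables. Footnote that values there come mostly from end-of-treatment visits, because no scheduled ACR falls within 8 weeks of escalation at a routine site visit. The column should not be read as the early response of all escalators.

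The cost is SAP wording, one extra category per display and one extra interval in the shift tables. No new data are needed. The picture of escalation may become slightly less favourable.
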